## **8. ADVERSE EVENTS**

### **8.0.1 Safety**

In non-randomised case series of patients with acute ischaemic stroke who were intubated and mechanically ventilated for cooling to 32°C or 33°C, pneumonia, arrhythmias, arterial hypotension, and thrombocytopenia were frequent complications. However, some of these complications may be attributed to the infarcts under trial, which were generally severe. In randomised trials of cooling to 32°C to 34°C after cardiac arrest, no differences in adverse effects were observed between the hypothermia and control groups. In a case-control trial of cooling to 35.5°C involving 17 patients, a mild decrease in blood pressure and heart rate were observed during hypothermia, as well as mild increases in haematocrit and the concentrations of haemoglobin, potassium, creatinin, albumin, and C-reactive protein. No serious adverse events were observed.

Reported side effects of pethidine include nausea, vomiting, constipation, drowsiness, and confusion. At higher doses, respiratory depression, arterial hypotension, and reduced level of consciousness have been reported.

### **8.0.2 Adverse Event Reporting**

The Investigator is responsible for the detection and documentation of events meeting the criteria and definitions detailed below.

Participants or their relative or welfare guardian will be instructed to contact their hospital doctor at any time after consenting to join the trial if any unexpected symptoms develop. All adverse events (AEs) that occur after joining the trial will be reported in detail in the CRF. In the case of an AE, the hospital doctor will initiate the appropriate treatment according to their medical judgment. Participants with AEs present at the last visit will be followed up until resolution of the event.

## 8.1 DEFINITIONS

An adverse event (AE) is any untoward medical occurrence in a clinical trial subject.

A serious adverse event (SAE) is defined by the National Research Ethics Service in the UK as any adverse event that:

- results in death
- is life threatening
- requires hospitalisation or prolongation of existing hospitalisation
- results in persistent or significant disability or incapacity
- is a congenital anomaly or birth defect.

## 8.2 DETECTING AND RECORDING AEs AND SAEs

All AEs and SAEs will be recorded from the time a participant consents to join the trial until the last trial visit. When an AE/SAE occurs, the Investigator will review all documentation (e.g. hospital notes) related to the event. The Investigator will then record all relevant information in the CRF and on the SAE form (if the AE meets the criteria of serious).

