#### 2.2.2 Secondary Endpoints

- Feasibility (recruitment rate; time to target temperature; stability at target; control of temperature during warming period)
- Tolerability (Columbia Shivering Score; patient questionnaire)
- Safety (deaths; adverse events including infections, DVT or coagulopathy; pethidine dose required)
- Oesophageal temperatures compared with tympanic, and bladder and/or rectal where available, at baseline, every 15 minutes in the first three hours after start of cooling and every 30 minutes thereafter until 48 hours after stroke onset
- Penumbra temperature 3 hours after initiation of cooling
- National Institutes of Health Stroke Scale (NIHSS) score, the Barthel Index (BI) and the modified Rankin scale (mRS) at three months
- Infarct volume on CT or MRI 7 days after the induction of hypothermia
- Temperature in ischaemic core, surrounding brain, and contralateral hemisphere determined using MR spectroscopy initiated 2-3 hours after the commencement of cooling
- Feasibility of collecting and processing samples for future biomarker study.

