### **6.0.3 Randomisation Through to Day 7 ( $\pm$ 1 day; or discharge, if earlier)**

1. Date and time of randomisation
2. Date and time of start of cooling
3. Level of consciousness, presence of shivering, rectal, bladder, and tympanic temperatures, blood pressure, and heart rate every 15 minutes in the first three hours after start of cooling, every 30 minutes thereafter until 12 hours after start of warming, and every 6 hours until day 7 (or discharge, if earlier)
4. Laboratory tests, including full blood count, serum glucose, electrolytes, PTT, aPTT, C-reactive protein, blood samples for biomarker and genetic studies. 12-lead electrocardiogram 6 and 12 hours after randomisation, and at 48 hours
5. NIHSS at 24 and 48 hours and at 7 days (or discharge, if earlier)
6. mRS and BI at day 7 (or discharge, if earlier)
7. Concurrent medication
8. Neurological and systemic adverse events
9. CT or MRI scan at day 7  $\pm$  2 days

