### **6.0.4 1 Month and 3 Months ( $\pm$ 14 days)**

Scores on the mRS, BI and NIHSS. To promote objective outcome assessment, a trial nurse will perform a standardised evaluation of each patient, including functional status, and will include the obtained information in an essay. Based on this essay, the members of the trial

steering committee who are blinded to treatment allocation, will determine the scores on the mRS and BI.

Serious adverse events (definition: see 8.1) during the trial period 7 days (or discharge, if earlier) through 3 months.

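### Sections 8.0.2 and 8.2 record all adverse events to the 3-month visit, but the section 6 schedule lists non-serious events only to day 7 or earlier discharge, and nothing says which governs

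*Protocol*

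**What the plan says.** Two parts of the protocol define when adverse events are recorded.

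- **Section 8 (adverse events).** Section 8.2: "All AEs and SAEs will be recorded from the time a participant consents to join the trial until the last trial visit". Section 8.0.2: "All adverse events (AEs) that occur after joining the trial will be reported in detail in the CRF". Neither mentions day 7 or discharge. Section 8.2 covers serious and non-serious events alike.
- **Section 6 (data collection).** The item "Neurological and systemic adverse events" is listed in 6.0.3 only. The heading of that section reads "Randomisation Through to Day 7" and allows an earlier close with the words "or discharge, if earlier". For the period after that, 6.0.4 lists "Serious adverse events (definition: see 8.1) during the trial period 7 days (or discharge, if earlier) through 3 months".

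The last scheduled assessment is the second of those in 6.0.4, headed "1 Month and 3 Months", with a tolerance of 14 days either way. The secondary endpoints in 2.2.2 include "adverse events including infections, DVT or coagulopathy", with no restriction to serious events.

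**The concern.** The two rules produce different safety data sets. Under section 8, every patient is observed for non-serious events for about three months. Under section 6, observation for those events stops within about a week, and sooner for a patient who goes home sooner. Site staff reading different sections would record different things, and an event that was never collected cannot be recovered at analysis.

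The discharge rule is the more troublesome part. Discharge happens after randomisation and could be affected by the allocated treatment. Cooled patients undergo 12 or 24 hours of cooling plus controlled rewarming (5.6.2), and section 5.6.3 accepts that they cannot take part equally in early mobilisation. A window that closes at discharge can therefore differ in length between arms, and an arm that stays longer can accumulate more recorded events at equal risk.

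The stakes are modest but real. Safety is part of the primary objective (2.1.1), section 7.1 compares 16 cooled patients with 8 controls to draw general conclusions about safety, and section 7.2 uses safety concerns in choosing the regimen for phase III. With 4 patients in each cooling arm, one event more or less moves a proportion by 1/4 = 25 percentage points; among 8 controls it moves it by 1/8 = 12.5 points. Data from other European pilots are to be combined with these (sections 3 and 7.1), so centres would also need a common rule.

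**Working it through.** The protocol states no figure on this point, so there is none to reproduce. The check sets the sections side by side and then compares window lengths.

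**Step 1: the rules compared**

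| | Sections 8.0.2 and 8.2 | Sections 6.0.3 and 6.0.4 |
|---|---|---|
| Start | Consent (8.2); joining the trial (8.0.2) | Randomisation |
| End, non-serious events | Last trial visit (8.2); no end stated (8.0.2) | Day 7 (± 1 day), or discharge if earlier |
| End, serious events | Last trial visit (8.2) | 3 months |
| Tied to discharge? | No | Yes, for non-serious events |

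For serious events the two schemes reach the same end. For non-serious events they do not. The period in 6.0.4 begins exactly where 6.0.3 closes, which reads as a two-stage scheme: all events first, serious events afterwards. The start points also differ, but both precede cooling, which 5.6.2 requires within 90 minutes of admission, so in cooled patients that gap is short.

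**Step 2: is there a tie-breaker?** None was found. Section 6 is introduced as the list of data to be collected in the case record file, and 8.0.2 and 8.2 also send events to the CRF, so neither part has stated priority. Section 8.5 and the end of 8.0.2 deal with events still present at the last visit. That fits either rule, because an event from the first week may persist.

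**Step 3: window lengths for non-serious events**

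Assumption: 3 months = 90 days; the 14-day tolerance gives 90 − 14 = 76 to 90 + 14 = 104 days.

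- Section 8.2 window: about 90 days (76 to 104).
- Section 6.0.3 window: the smaller of 7 days and time to discharge.
- Full section 6.0.3 window as a share of the section 8.2 window: 7/90 = 8% (7/104 = 7% to 7/76 = 9%).

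**Step 4: effect of early discharge if section 6.0.3 is followed**

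The discharge days below are illustrations; the protocol gives none. Share = discharge day / 7.

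| Discharge on day | Observation time relative to a patient still in hospital on day 7 |
|---|---|
| 2 | 2/7 = 29% |
| 3 | 3/7 = 43% |
| 5 | 5/7 = 71% |
| 7 or later | 100% |

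These are ratios of observation time for individual patients. They are not estimates of a difference between arms, which would need lengths of stay by arm and the timing of events, and the protocol has neither.

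**The case against.** The strongest reply is that section 8 is the dedicated adverse-event section and is clear, so section 6 can be read as a visit schedule running alongside continuous reporting. Section 6.0.4 lists serious events without expressly excluding others. Section 8.0.2 also tells participants or relatives to contact their hospital doctor about unexpected symptoms at any time, so a route for events after discharge exists. This reading is possible, and if it is the intended one every patient has the same window. But the protocol does not say so, the route is passive, and the schedule asks for nothing beyond serious events at the 1- and 3-month contacts.

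A reader might go further and infer several things that the protocol does not support:

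- **That non-serious event counts do depend on length of stay.** This follows only if section 6 is applied and some patients leave before day 7.
- **That the comparison is biased against cooling by a known amount.** A figure could be obtained by assuming a constant daily event rate and certain lengths of stay, but the protocol supplies neither. A constant rate is also doubtful for an intervention of 12 or 24 hours plus rewarming. If treatment-related events cluster early, most fall inside either window.
- **That all the listed safety outcomes are exposed.** Skin reactions under the cooling pads cannot arise in uncooled controls, so length of stay cannot distort that comparison. An infection or thrombosis that leads to or prolongs a hospital stay is serious under 8.1 and is followed to 3 months in both schemes. What remains exposed is milder events, such as a minor infection after early discharge.

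It is also fair that adverse events are a secondary endpoint, the primary endpoint is completion of the intervention, and the analysis is mainly descriptive (7.2). This limits the consequence but does not remove the contradiction.

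**Conclusion.** The contradiction stands: for non-serious adverse events, sections 8.0.2 and 8.2 give one recording period, sections 6.0.3 and 6.0.4 give another, and no text decides between them. The gap is large in time, about 7 days against about 90, with 3 months taken as 90 days. Serious events are unaffected apart from the short difference in start point.

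The dependence on length of stay is conditional. It arises if section 6 is the operating rule and patients are discharged before day 7. In that case recorded counts could differ between arms with no difference in risk. Because the protocol gives no lengths of stay, neither size nor direction can be stated. This should be corrected, mainly because safety belongs to the primary objective and the correction is cheap; nothing here shows that the trial's safety comparison is in fact biased.

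**What to change.** Reconcile 6.0.3, 6.0.4, 8.0.2 and 8.2 to one adverse-event window with the same start and end in every arm, not tied to discharge. The simplest version keeps section 8.2 as written: list all adverse events in 6.0.4 as well, and add an adverse-event question at the existing 1- and 3-month contacts. Alternatively, name one fixed calendar day in all four sections for non-serious events, and obtain those occurring after discharge at the 1-month contact. State one start point, either consent or randomisation. Use the chosen window for all comparisons between arms, and put the same rule to the other European pilots so that pooled counts are comparable.

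The cost is an amendment to protocol and CRF wording and a little extra data entry at contacts that already take place.

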## 8.3 EVALUATION OF AEs AND SAEs

The investigator must make an assessment of whether the SAE is likely to be related to the treatment according to the following definitions:

Unrelated	where an event is not considered to be related to the treatment
Possibly	although the relationship to the treatment cannot be ruled out, the nature of the event and/or underlying disease make other definitions possible
Probably	the relationship and absence of a more likely explanation suggest the event could be related to the intervention
Definitely	the known effects of therapeutic hypothermia suggest that this is the most likely case of the event

### 8.3.1 Assessment of Severity

The Investigator should make an assessment of severity for each AE/SAE and record this on the CRF according to one of the following categories:

Mild	an event that is easily tolerated by the participant, causing minimal discomfort and not interfering with every day activities.
Moderate	an event that is sufficiently discomforting to interfere with normal everyday activities.
Severe	an event that prevents normal everyday activities.

Note: the term 'severe', used to describe the intensity, should not be confused with 'serious' which is a regulatory definition based on participant/event outcome or action criteria. For example, a headache may be severe but not serious, while a minor stroke is serious but may not be severe.

## 8.4 REPORTING OF SAEs

As soon as the investigator becomes aware that an SAE has occurred in a trial participant, they must report the information to the Academic and Clinical Central Office for Research & Development (ACCORD) office in Edinburgh within 24 hours. The SAE form must be completed as thoroughly as possible with all available details of the event and must be signed by the investigator. If the investigator does not have all the information regarding an SAE, they should not wait for this additional information before notifying the ACCORD office. The form can be updated when additional information is received. The SAE report must contain details of the causality and expectedness at the time of initial report to the ACCORD office.

The SAE form should be transmitted by fax to the ACCORD office central office on [name].

#### **8.5 FOLLOW UP PROCEDURES**

After initially recording an AE or recording and reporting an SAE, the Investigator is required to follow each participant until resolution. Follow up information on an SAE should be reported to the ACCORD office on resolution.

AEs still present in participants at the last trial visit should be monitored until resolution of the event or until no longer medically indicated.

#### **9. PREGNANCY**

Pregnancy. Women of childbearing potential are excluded unless a negative test for pregnancy has been obtained prior to randomisation.

#### **10. TRIAL MANAGEMENT AND OVERSIGHT ARRANGEMENTS**

##### **10.1 PROJECT MANAGEMENT GROUP**

The trial will be coordinated by a Project Management Group, consisting of the grant holders, Chief Investigator and a Trial Co-ordinator. Coordination of the trial across European centres will be through the European Stroke Research Network for Hypothermia (ESRNH), who will appoint an International Trial Steering Committee.

##### **10.2 TRIAL MANAGEMENT**

A Trial Co-ordinator will oversee the trial and will be accountable to the Chief Investigator. The Trial Co-ordinator will be responsible for checking the CRFs for completeness, plausibility and consistency. Any queries will be resolved by the Chief Investigator or delegated member of the trial team.

A Delegation Log will be prepared, detailing the responsibilities of each member of staff working on the trial.

##### **10.3 CENTRAL TRIAL OFFICE**

The Central Trial Office is based in the University of Edinburgh. The office will be responsible for randomisation, collection of data, data processing and analysis.

Publication and dissemination of the trial results will be coordinated by ESRNH in collaboration with the Chief Investigator and Investigators.

##### **10.4 TRIAL STEERING COMMITTEE**

A Trial Steering Committee (TSC) will be established to oversee the conduct and progress of the trial. The names of the TSC members and their roles are detailed in Appendix 1.

##### **10.5 DATA MONITORING COMMITTEE**

An independent Data Monitoring Committee (DMC) will be established to oversee the safety of subjects in the trial. The DMC will oversee the pilot studies in all centres, not just in Edinburgh. The names of the DMC members are detailed in Appendix 2.

##### **10.6 INSPECTION OF RECORDS**

Principal Investigators and institutions involved in the trial will permit trial related monitoring, audits, Regional Ethics Committee (REC) review, and regulatory inspection(s). In the event of an audit, the Investigator agrees to allow the Sponsor, representatives of the Sponsor or regulatory authorities direct access to all trial records and source documentation.

## **11. GOOD CLINICAL PRACTICE MODULE**

### **11.1 ETHICAL CONDUCT OF THE TRIAL**

The trial will be conducted in accordance with the principles of the International Conference on Harmonisation Tripartite Guideline for Good Clinical Practice (ICH GCP).

A favourable ethical opinion will be obtained from the appropriate REC and local R&D approval will be obtained prior to commencement of the trial.

### **11.2 INVESTIGATOR RESPONSIBILITIES**

The Investigator is responsible for the overall conduct of the trial at the site and compliance with the protocol and any protocol amendments. In accordance with the principles of ICH GCP, the following areas listed in this section are also the responsibility of the Investigator. Responsibilities may be delegated to an appropriate member of trial site staff. Delegated tasks will be documented on a Delegation Log and signed by all those named on the list.

#### **11.2.1 Informed Consent**

Written informed consent for this trial must be obtained from the patient or their nearest relative or welfare guardian (if the patient is not capable of giving consent) prior to the performance of any protocol-specific procedure. However, several assessments or tests described in the protocol may have been performed as part of the patient's routine clinical evaluation (i.e. not specifically performed for this trial). A copy of the written informed consent must be given to the subject, their family doctor and a copy held in the trial patient file.

The Investigator is responsible for ensuring informed consent is obtained before any protocol specific procedures are carried out. The decision of a participant, or their relative or welfare guardian, to participate in clinical research is voluntary and should be based on a clear understanding of what is involved.

Participants will receive adequate oral and written information – appropriate Participant Information and Informed Consent Forms will be provided. The oral explanation to the participant should be performed by the Investigator or designated person, and must cover all the elements specified in the participant Information Sheet/Informed Consent.

The participant will be given every opportunity to clarify any points they do not understand and, if necessary, ask for more information. The participant will be given sufficient time to consider the information provided. Because of the short time window for trial inclusion and treatment, this will be in the order of 10 to 15 minutes. It will be emphasised to the participant or their relative or welfare guardian that they may withdraw their consent to participate at any time without loss of benefits to which they otherwise would be entitled.

#### **11.2.2 Trial Site Staff**

The Investigator will be familiar with the protocol and the trial requirements. It is the Investigator's responsibility to ensure that all staff assisting with the trial are adequately informed about the protocol and their trial related duties.

#### **11.2.3 Data Recording**

The Investigator is responsible for the quality of the data recorded in the CRF.

#### **11.2.4 Investigator Documentation**

The Trial Office will ensure all other documents required by the principles of ICH GCP are retained in a Trial Master File and that appropriate documentation is available in a local Investigator Site File.

#### **11.2.5 GCP Training**

All trial staff will hold evidence of appropriate GCP training or undergo GCP training. This should be updated every two years throughout the trial.

#### **11.2.6 Confidentiality**

All laboratory specimens, evaluation forms, reports, and other records will be identified in a manner designed to maintain participant confidentiality. All records will be kept in a secure storage area with limited access. Clinical information will not be released without the written

permission of the participant, except as necessary for monitoring and auditing by the Sponsor, its designee, Regulatory Authorities, or the REC. The Investigator and trial site staff involved with this trial will not disclose or use for any purpose other than performance of the trial, any data, record, or other unpublished, confidential information disclosed to those individuals for the purpose of the trial. Prior written agreement from the Sponsor or its designee will be obtained for the disclosure of any said confidential information to other parties.

#### 11.2.7 Data Protection

All UK Investigators and trial site staff involved with this trial will comply with the requirements of the Data Protection Act 1998 with regard to the collection, storage, processing and disclosure of personal information and will uphold the Act's core principles. Access to collated participant data will be restricted to those clinicians treating the participants.

Computers used to collate the data will have limited access measures via user names and passwords.

Published results will not contain any personal data that could allow identification of individual participants.

## **12. TRIAL CONDUCT RESPONSIBILITIES**

### 12.1 PROTOCOL AMENDMENTS

Any changes in research activity, except those necessary to remove an apparent, immediate hazard to the participant, must be reviewed and approved by the Chief Investigator. Amendments to the protocol must be submitted in writing to the appropriate REC, Regulatory Authority and local R&D for approval prior to participants being enrolled into an amended protocol.

